#### Include:

- 1) The incidence of symptomatic intracranial hemorrhage within 36 hours (as defined by ECASSIII)
- 2) The incidence of symptomatic intracranial hemorrhage within 90 days (as defined by ECASSIII)
- 3) The incidence of PH2 intracranial hemorrhage within 36 hours (according to SITS standards)
- 4) The incidence of any intracranial hemorrhage within 90 days
- 5) The incidence of significant hemorrhage events at other sites within 90 days (as defined by GUSTO)
- 6) 90-day overall mortality
- 7) Incidence rates of adverse events/serious adverse events within 90 days;

The analysis of the primary safety endpoints refers to the general statistical analysis principles. The number and incidence of various bleeding events and adverse events in the primary safety endpoints are described. The incidence of events between the two groups is compared using the chi-square test or Fisher's exact probability method, and a 95% confidence interval for the difference in incidence between the groups is calculated.

Other safety endpoints:

## (1) Adverse events

The number of cases and events of AE, adverse reactions, AE causing drop-out and SAE are calculated respectively, and a detailed list is provided. The incidence is calculated using the number of people in each safety dataset as the denominator, and the Chi-square test or Fisher's exact probability method is used for inter-group comparison when necessary.

The number of cases and events of the events mentioned in the above endpoints are counted according to the systematic organ classification and preferred terms encoded by MEDDRA, as detailed in the Statistical Analysis protocol (SAP).

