### 11. Sample size

In this study, rt-PA active control will be used based on a statistical hypothesis test of non-inferiority, and the proportion of subjects with 90-day MRS score of 0-1 will be used as the primary efficacy endpoint.

According to a paper published in the Lancet[7] in 2014 about meta-analysis of the incidence of 90-day MRS score of 0-1 (treatment within 4.5h) regarding rt-PA versus Placebo, the RR and 95% confidence interval were 1.24 and 1.14-1.36, respectively. According to the Guidelines for the Design of Non-inferiority Drug Clinical Trials [32], the lower 95% confidence interval of the Meta analysis should be used to calculate the non-inferiority threshold given that the primary endpoint is a high priority index. Therefore, based on the lower CI limit of 1.14, together with an efficacy of 50% of the active control, the non-inferior threshold was determined as 0.937. Then assuming  $\alpha$ =0.025 using one-sided test, power 1- $\beta$ =0.85, treatment group (TNK) incidence of 63.64%, control group (rt-PA) incidence of 59.32%, RR= 1.07, the sample size was calculated to be 642 cases in each group; considering a dropout rate of 10%, the sample size was determined as 715 cases in each group and the total sample size is estimated to be 1430 cases.

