#### 12. Statistical plan

## 12.1 Statistical analysis

Full analysis set (FAS), per protocol set (PPS) and safety analysis set (SAS) will be established according to the NMPA regulations for data statistical analysis. Strict quality control will be carried out in the whole process of data collection to ensure the authenticity of the evaluation data.

Full analysis set (FAS): a data set consisting of all subjects randomized to receive at least one study drug according to the basic principle of Intention To Treat.

Per protocol set (PPS): PPS includes all subjects who complete the stipulated treatment without missing primary efficacy endpoints or serious violations of the protocol. Serious protocol violation will be finally defined during data review and

may generally include (but not limited to) the following situations: subjects violating inclusion criteria or exclusion criteria, poor compliance in stipulated medication, concomitant medication that affects outcome indicators, and out of visit window.

Safety analysis set (SS): a set of all subjects participating in the trial, receiving at least one study drug, and having at least one safety evaluation.

FAS and PPS are established as sensitive analysis groups; Efficacy analysis is performed on the basis of FAS and PPS. Safety endpoints will be performed on the safety set and safety missing data will not be filled. All baseline demographic data analyses will be performed on the basis of the FAS; illogic data needs to be investigated by the data management facility, investigators or Sponsor together to identify possible reasons, and restrained by the parties in a data review meeting after full discussion: illogic data, if sufficient reasons have been found to indicate its incorrectness, should be removed, or otherwise, should be remained and subjected to analysis and the results obtained without such removed data should be treated as sensitivity analysis; If there is data collected in the study that is not in accordance with the program requirements such as planned external visits, it will be presented in a list, and descriptive or comparative analysis will be decided at the data review meeting depending on the specific situation of the data.

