#### Safety Set (SS)

All patients who received at least 1-time of study drug according to the study protocol and safety assessment available will be included in the safety population. Throughout the safety results sections, erroneously treated patients (eg, those randomized to rhTNK-tPA group but actually given rhTNK-tPA) will be accounted for in the actual treatment group. This population will be used for safety analyses.

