#### 10. Data handling conventions

#### Premature Withdrawal and Missing Data

If any subject withdraws prematurely from the study (prior to the final visit D90±7 days assessment), they are required to complete the withdrawal visit in the CRF. The reasons for withdrawal will be presented in a summary table. For the purposes of summaries and analysis of clinic visit data, this visit will be assigned to the next scheduled clinic visit for that patient, regardless of whether the date falls within the next visit window.

Patients who withdraw before the end of the study, but who do provide at least one post-baseline measure for a particular endpoint, will be included in the analysis.

Patients who do not attend any visits after randomization will be excluded from analysis of efficacy outcomes and safety outcomes, as no post-baseline data will be available.

Missing data will not be imputed in the main analysis. Illogic data needs to be investigated by the data management facility, investigators or Sponsor together to identify possible reasons, and restrained by the parties in a data review meeting after full discussion: illogic data, if sufficient reasons have been found to indicate its incorrectness, should be removed, or otherwise, should be remained and subjected to analysis and the results obtained without such removed data should be treated as sensitivity analysis; If there is data collected in the study that is not in accordance with the program requirements such as planned external visits, it will be presented in a list, and descriptive or comparative analysis will be decided at the data review meeting depending on the specific situation of the data. In sensitivity analysis, multiple imputation was performed to impute the missing data of the primary efficacy outcome.

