#### **Event Rates**

The number of people of events should be recorded in detail and showing the event rate in 90 days of each treatment group in summary statement.

The event rate for each treatment group will be calculated as: the sum of number of event for all the patients / the number of patients enrolled in this group.

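### As written, the safety rules count a treated patient whose day-90 vital status is unknown as a non-death, so 90-day mortality is modestly understated under loss to follow-up, and the safety denominators need reconciling

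*Supplement*

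**What the plan says.** Four rules in the latest documents bear on this.

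- **Population.** SAP section 13 runs all safety analyses on the Safety Set. Under SAP section 7, patients who "received at least 1-time of study drug according to the study protocol and safety assessment available will be included in the safety population". Neither a post-dose scan nor a known vital status at day 90 is required.
- **Missing data.** Protocol section 12.1: "Safety endpoints will be performed on the safety set and safety missing data will not be filled". SAP section 10: "Missing data will not be imputed in the main analysis". The one missing-data sensitivity analysis concerns efficacy: "multiple imputation was performed to impute the missing data of the primary efficacy outcome".
- **Denominator.** SAP section 10, Event Rates, gives the rate in 90 days as "the sum of number of event for all the patients / the number of patients enrolled in this group". Protocol section 12.5 has a different denominator under Other safety endpoints, item (1) Adverse events: "The incidence is calculated using the number of people in each safety dataset as the denominator". For the primary safety endpoints, which include 90-day mortality and the hemorrhage endpoints, section 12.5 names no denominator.
- **Comparison.** Protocol section 12.5, for the primary safety endpoints: "The incidence of events between the two groups is compared using the chi-square test or Fisher's exact probability method", with a confidence interval for the difference in incidence.

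SAP section 10 also excludes patients with no visit after randomization, keeps withdrawn patients who have at least one post-baseline measure for the endpoint in question, and moves a withdrawal visit to the next scheduled visit whatever its date. Protocol section 11 allows for loss: "considering a dropout rate of 10%, the sample size was determined as 715 cases in each group".

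**The concern.** A proportion with a fixed full denominator and only observed events in the numerator treats every unknown as a non-event. For 90-day mortality, a treated patient who is lost on day 10 is counted with the survivors. The withdrawal-visit rule works in the same direction: a patient who withdraws alive on day 20 can fill the day-90 slot.

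Mortality and intracranial hemorrhage are primary safety endpoints, and the safety case for a thrombolytic rests on them. The plan tests the sensitivity of the efficacy result to missing data but plans no such check for harm. It has no time-to-event analysis of death, no known-status denominator, no worst-case analysis, and no rule for unknown vital status or a missing 24-36 h scan. Treatment is open label, so loss that differs between arms cannot be ruled out in advance.

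**Working it through.** **The plan's own figure.** The documents give no expected safety incidence and no expected rate of missing safety data. The figure that can be reproduced is the sample size (protocol section 11, SAP section 6). On the log relative-risk scale, with control rate 0.5932, RR 1.07 (treatment rate 0.5932 x 1.07 = 0.6347), margin 0.937, one-sided alpha 0.025 and power 0.85:

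n = [(1 - 0.6347)/0.6347 + (1 - 0.5932)/0.5932] x (1.960 + 1.036)^2 / [ln(1.07/0.937)]^2 = 642.8 per arm

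The plan states 642. Allowing for 10% dropout, 643/0.9 rounds up to the stated 715. The sample size is not affected by this point; 715 per arm and 10% are used below only for illustration.

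**Mortality: inputs.** The protocol's literature overview (section 1.3) quotes 90-day mortality of 5% in each arm of one tenecteplase-alteplase trial, and mortality of 7.7% for alteplase in the placebo-controlled 3-4.5 h trial. The loss fraction, the timing of loss and any imbalance between arms are assumptions.

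**Mortality: formula.** Reported risk = true risk x (1 - fraction lost x share of the lost patients' death risk that falls after loss). If the whole risk falls after loss, this reduces to true risk x (1 - fraction lost).

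- 10% lost, 30% to 90% of the risk after loss: 7.7% x 0.97 = 7.47%; 7.7% x 0.91 = 7.01%.
- 10% lost, all of the risk after loss: 7.7% x 0.90 = 6.93%; 5% x 0.90 = 4.50%.
- 2%, 5% or 10% lost, all of the risk after loss: the reported rate is 0.98, 0.95 or 0.90 of the rate among patients with known status.
- Worst case, 10% lost and all of them dead: 6.93% + 10% = 16.9%; 4.50% + 10% = 14.5%.
- Lost patients dying at twice the rate of those observed: true risk 0.9 x 7.7% + 0.1 x 15.4% = 8.47%, against 6.93% reported.

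**Comparison between arms, equal true risks of 7.7%.**

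- Equal loss of 10%: 6.93% v 6.93%, RR 1.00.
- 5% v 15% lost, all of the risk after loss: RR = 0.95/0.85 = 1.118, or 0.895 if reversed; spurious difference 7.7% x 0.10 = 0.77 points.
- 5% v 15% lost, 30% to 90% of the risk after loss: spurious difference 0.23 to 0.69 points.

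If the true risks do differ, equal loss unrelated to outcome leaves the RR unchanged and shrinks the risk difference by the fraction lost.

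**Hemorrhage.** Assume 0.5-2% of 715 per arm have no post-dose scan (4 to 14 patients) and 30-50% of them bled. Then 715 x 0.005 x 0.30 = 1.1 to 715 x 0.02 x 0.50 = 7.2 bleeds per arm go uncounted. The 3-4.5 h trial in section 1.3 reports any intracranial hemorrhage in 27.0% of alteplase patients. That would be 715 x 0.27 = 193 per arm, so the shortfall is 0.6% to 3.7% of that endpoint. The documents quote no PH2 rate, so the relative effect on PH2 cannot be sized.

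**The case against.** The strongest reply is that the plan never says lost patients are alive or unscanned patients free of hemorrhage. On this reading, leaving missing data unfilled means just that, and scoring an unknown as a non-event would itself be filling. The adverse-event denominator in protocol section 12.5 governs AE and SAE incidence, where a treated-population denominator is ordinary practice. A reader might infer that it also governs mortality and hemorrhage; the documents do not say so. The SAP's endpoint-specific inclusion rule can be read as dropping a withdrawn, never-scanned patient from the imaging endpoints.

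There are also safeguards. Protocol section 9.7 and Appendix 1 call for immediate imaging on neurological symptoms or worsening. The sICH definition covers bleeding that led to death. An independent committee verifies events from clinical, laboratory, imaging or other records. Investigators must try to complete the last examination for drop-outs and patients lost to follow-up. The 10% is a sample-size allowance, and the protocol's drop-out category includes patients who merely decline further medication and testing, so it is not a forecast of unknown vital status.

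Much of this stands. The outcome scoring is a consequence of the arithmetic, not a stated rule, and the loss and non-scanning figures are assumptions. The imaging safeguards should keep unscanned bleeds few.

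It does not clear mortality. The SAP event-rate formula is the only explicit 90-day denominator, and it covers everyone enrolled in the arm. The endpoint-specific rule does not help either: a patient last seen alive on day 7 stays in. Nor does it reach patients who die unscanned without having withdrawn.

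**Conclusion.** The point holds for 90-day mortality. As written, unknown vital status counts as non-death, and reported mortality falls short by up to the fraction lost when loss is unrelated to outcome, and by more if lost patients fare worse. At an assumed 10% loss, 7.7% becomes about 6.9-7.5%, a shortfall of roughly 0.2 to 0.8 percentage points. That is modest, and proportionally smaller if fewer are lost.

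A reader might go further and infer that the treatment comparison is biased or that the arms are pulled together. The documents do not support that. Bias needs loss that differs by arm or is related to outcome, and nothing in the plan shows either; equal loss unrelated to outcome leaves the RR at 1.00. A reader might also infer a large undercount of hemorrhage by setting 1 to 7 missed bleeds against the 17 or so sICH expected at the quoted 2.4% (715 x 0.024 = 17.2). For any intracranial hemorrhage the relevant comparator is about 193 per arm, missed bleeds need not be symptomatic, and the symptom-triggered scan works against that reading.

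What remains is a gap in pre-specification for primary safety endpoints, with denominators that disagree between the protocol and the SAP. It is worth mending, and it does not threaten the trial.

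**What to change.** Amend protocol section 12.5 and SAP sections 10 and 13.

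1. **Mortality.** In the Safety Set, estimate the risk of death at day 90 per arm by Kaplan-Meier, censoring at the last date known alive, and report the risk difference with 95% CI. Report the number with unknown vital status by arm. Because censoring assumes uninformative loss, add a worst-case sensitivity analysis that counts unknowns as deaths. State when a patient seen at the early edge of the 90±7 day window counts as known.
2. **Hemorrhage.** Keep the Safety Set denominator as the main analysis and leave the definition of any intracranial hemorrhage within 90 days as it is. Report the number without a post-dose scan by arm. Add two sensitivity analyses: one restricted to scanned patients, and one counting treated patients who died unscanned as bleeds. Both are needed, since a scanned-only denominator drops exactly those early deaths.
3. **Denominators.** Choose one base for safety rates. Reconcile the SAP Event Rates formula (all enrolled), the Safety Set rule in SAP section 13, the endpoint-specific inclusion rule in SAP section 10 and the AE denominator in protocol section 12.5. Say that a withdrawal visit moved to day 90 does not establish day-90 vital status.

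The cost is SAP wording and a few tables, with a second denominator appearing in the safety output. The protocol has the timing of adverse events recorded and deaths reported. It does not name a last-known-alive field, so the team should confirm that this date can be derived from visit and contact records.

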## 2 Evaluation of laboratory test indicators

Include routine blood test, routine urinalysis, blood biochemistry and lipid indexes.

The number of cases is described for each kind of clinical judgment result (normal, abnormal without clinical significance, abnormal with clinical significance and not tested) of laboratory examination results before and after treatment in the form of a cross table.

The patients who are judged to be abnormal after the treatment are described in detail by nature (with clinical significance, without clinical significance, or not tested) in the form of lists.

## ③ Evaluation of vital signs

The mean, standard deviation, median, minimum and maximum are used to describe the changes of vital signs from each visit to the baseline.

## (4) Evaluation of physical examination

The physical examination results of each visit are described and the number and percentage of normal and abnormal cases are calculated.

## 5 ECG evaluation

Refer to the evaluation section of laboratory examination indicators.

## 13. Ethics and regulatory procedures

### 13.1 Ethical principles

This study protocol has been rigorously reviewed. It contains information that is consistent with current knowledge of the risks and benefits of test drugs and is consistent with the ethical, ethical and scientific principles of clinical trials set out in the *Declaration of Helsinki* 2013, as well as the guidelines of Chinese *Good Clinical Practice*.

### 13.2 Laws and regulations

The management of this clinical trial will be in accordance with international laws and regulations, and the laws and regulations of China where the trial is conducted, as well as any guidelines on its application.

#### 13.3 Informed consent

Informed consent obtaining is the process by which subjects confirm their consent to voluntarily participate in the clinical trial after being informed of all aspects that may influence their decision to participate in the trial. This process shall be documented by a written, signed and dated informed consent.

To implement informed consent, investigators should abide by the ethical principles of the *Declaration of Helsinki* and meet the following requirements:

- (1) The investigator shall use the latest version of the informed consent form approved by the IRB and other information provided to the subject. If necessary, subjects during the clinical trial should re-sign the informed consent.
- (2) When the investigator obtains new information that may affect the continued participation of subjects in the study, he/she shall timely inform the subjects or their guardians and make corresponding records.
- (3) The investigator shall not influence the subjects to participate in or continue the clinical trial by coercion, inducement for profit or other improper means.
- (4) The Investigator or the designated study-related personnel shall fully inform subjects of all matters related to the clinical trial, including written information and the consent of the IRB.
- (5) Informed consent form and other oral and written information provided to the subjects shall be easy to understand, so that the subjects or their guardians and witnesses can easily understand.
- (6) Before signing the informed consent, the investigator or the designated study-related personnel shall give sufficient time and opportunity for subjects or their guardians to understand the detailed information of the clinical trial and answer questions raised by subjects or their guardians in detail related to the clinical trial.
- (7) The subject or his/her guardian, as well as the investigator performing the informed consent shall sign and indicate the date on the informed consent. If not signed by the subject, the relationship shall be indicated.
- (8) If the subject or his/her guardian lacks reading ability, an impartial witness should be present to witness the whole informed consent process. The investigator

shall explain in detail the contents of the informed consent and other written materials to the subjects or their guardians and witnesses. Such as participants or their guardians oral agreed to participate in the trial, in the case of ability should sign the informed consent, as witnesses shall also sign the informed consent form and indicate the date, to prove that the participants or their guardians of informed consent and other written materials investigators accurately explain, and understand the relevant content, agreed to participate in clinical trials.

- (9) The subject or his/her guardian shall receive the signed and dated original or copy of the informed consent and other written information provided to the subject, including the original or copy of the updated informed consent and the revised version of other written information provided to the subject.
- (10) If the subject has no capacity for civil conduct, it shall obtain the written informed consent of its guardian; If the subject is a person with limited capacity for civil conduct, the subject shall obtain the written informed consent of the subject and his/her guardian. When the guardian gives informed consent on behalf of the subjects, the guardian shall inform the subjects of the relevant information of the clinical trial to the extent understandable to the subjects, and try to have the subjects personally sign the informed consent and indicate the date.
- (11) Under emergency circumstances, if informed consent of subjects cannot be obtained before participating in the clinical trial, their guardians can give informed consent on behalf of the subjects. If their guardians are not present, the method of enrollment of subjects shall be clearly stated in the trial protocol and other documents, and written consent of the ethics committee shall be obtained; At the same time, informed consent should be obtained as soon as possible for subjects or their guardians to continue to participate in the clinical trial.
- (12) The specific time and personnel of informed consent of the subject shall be recorded in the medical history.
- (13) Informed consent should be given in the research center to avoid infringement/disclosure of the subject's privacy.

